6.3 Criteria for Stopping/Study Withdrawal

Study participation will continue for up to 3 years or until

- withdrawal of consent by the patient or legal guardian
- the patient is lost-to-follow-up
- death
- data collection ends

A patient may also be discontinued from the study for the following medical or administrative reasons:

- Noncompliance, including failure to adhere to the study requirements
- The Sponsor terminates the study

One missed survey completion in the period of 1 year will automatically withdraw the patient from the study, unless otherwise indicated the patient will be categorized as lost-to-follow up.

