If the study team is unsuccessful in reaching the patient, the patient will be considered lost-to-follow up and the study team will update the enrollment status as appropriate.

Upon completion of the electronic consent and successful enrollment, the patient will be prompted to complete an online survey at Baseline, then every 6 months for a period of up to 3 years. All surveys will be completed online, at the patient's convenience, and in accordance with [Appendix A](#). The study team will provide technical support and reminder prompts, as described above, throughout the duration of participation.

At any time after Baseline, if the study team is unable to reach a patient after 3 attempts and the patient does not complete the survey within the prespecified window, the patient will be considered lost-to-follow up and the study team will disable the patient's unique study link as appropriate. Awareness by the specialty pharmacy of any change in the patient's status (ie, withdrawal of consent, treatment discontinuation) must be communicated to the study team. Should the specialty pharmacy communicate a patient's status change during the 3-year Follow-up Period, the study team will disable the patient's unique study link upon notification and no further survey invitations or reminders will be triggered.

Information regarding a patient's initial prescription and refill(s) will also be collected from the specialty pharmacies for all enrolled patients.

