5.1.1 Survey Conduct

An electronic consent and survey questionnaire approved by an Institutional Review Board (IRB) will be used by RTI to program the online survey for the purpose of standardizing responses among patients.

Each patient will complete up to 7 web-based surveys over the duration of the study. Each survey is anticipated to take no more than 20 minutes on average.

All assessments, except mortality, will be patient-reported; medical records will not routinely be requested or reviewed as part of this observational study unless required for safety reporting purposes. As patient recall over time may be limited, partial responses as in the case of dates of onset, and/or estimates of numerical information will be accepted.

Participation in the study is contingent on continued use of XERMELO. Each survey will establish ongoing treatment with XERMELO and continued consent to study participation prior to subsequent data collection.

The initial survey is intended to gather Baseline information, which may include:

- Sociodemographics (age, year of birth, sex, race, ethnicity, education, geographic region)
- Current medical history as it relates to CS, NET burden, NET location, and related conditions
 - Location of NET
 - Date of diagnosis; CS and NET
 - CS-related hospitalization(s)
 - CS-related ER visit(s)
 - NET-related surgery (eg, tumor debulking, lysis of adhesions)
- Satisfaction with CS, CS-related diarrhea and/or flushing control prior to starting XERMELO, where applicable
- Height and weight
- Concomitant medication as it relates to the following:
 - Long-acting SSA therapy

- Use of rescue medication - short-acting SSA
- Systemic tumor-directed therapy
- Liver-directed therapy (eg, chemoembolization)
- WPAI-SHP

The initial survey should be completed no later than 30 days, and subsequent surveys should be completed no later than 14 days, after the unique survey link has been provided to the patient via e-mail. Patients will be asked to complete a survey every 6 months for up to 3 years. The following patient-reported data may be collected as described in [Appendix A](#):

- Satisfaction with CS, CS-related diarrhea and/or flushing control after initiating XERMELO, where applicable
- PGIC
- Concomitant medication as it relates to the following:
 - Change in use of rescue medication - short-acting SSA
 - Change in long-acting SSA therapy
 - Systemic tumor-directed therapy
 - Liver-directed therapy (eg, chemoembolization)

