3.2.5 Work Productivity and Activity Impairment Questionnaire—Specific Health Problem (WPAI-SHP)

The WPAI-SHP is a self-administered questionnaire ([Reilly et al., 1993](#)) comprising 6 questions that measure the effect of health problems on participants' ability to work and participate in regular activities based on their experiences in the previous 7 days. This questionnaire will be administered at Baseline and at the initial 6-month Follow-up.

The WPAI-SHP includes 4 domains (absenteeism, presenteeism, work productivity loss, and activity impairment). All participants will be asked whether they are employed (Q1) and how their CS-related problems affected their regular activities (Q6). Employed participants will be asked about hours of work missed due to CS-related problems (Q2), hours of work missed for any reason (eg, vacation, holidays, time off to participate in this study) (Q3), hours actually worked (Q4), and the degree that CS affected their productivity while working (Q5). An integer scale from 0 to 10 is used for Q5 and Q6, where 0 corresponds to no effect and 10 corresponds to complete effect.

Responses to the items are scored to produce the following 4 domains:

- Absenteeism: work time missed due to CS = [REDACTED]
- Presenteeism: impairment while working due to CS = [REDACTED]

- Work productivity loss: overall work impairment due to CS = [REDACTED]
[REDACTED]
- Activity impairment: activity impairment due to CS = [REDACTED]

Each score is then multiplied by 100 to express domains in terms of impairment percentages, with higher numbers indicating greater impairment and less productivity (ie, worse outcomes).

3.2.6 *Carcinoid Syndrome-related Health Care Resource Utilization*

At Baseline and at each Follow-up, questionnaire items will ask patients about ER visits and hospitalizations during the prior 6-month period. Data collected will include the following:

- The number of ER visits and the CS-related reason for each visit
- The number of hospitalizations, the number of nights for each stay, and the CS-related reason for each hospitalization

3.2.7 *Study Discontinuation and Mortality*

Patients will be terminated from the study if they discontinue the use of XERMELO, withdraw consent for participation, or are lost to follow-up. Information on reasons for discontinuation will be provided by the specialty pharmacy.

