Information on patient deaths during the study will be collected by the specialty pharmacy and transferred to RTI-HS for analysis. This information may be aggregated (ie, counts of patients who die during each 6-month interval) or patient-level, with or without actual dates of death.

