5.1.5 Other Endpoint Analyses

5.1.5.1 Analyses of Incidence of Emergency Room Visits, Hospitalizations, and Mortality

Incidence proportions for patients with at least 1 ER visit, at least 1 hospitalization, and mortality during each 6-month Follow-up interval will be reported along with 95% CLs. The denominator for each incidence proportion will be the number of patients enrolled in the

study at the beginning of that particular 6-month interval who also provide a non-missing response to the questionnaire item for each type of event.

The time to the first occurrence of a CS-related ER visit, time to the first occurrence of a CS-related hospitalization, time to the first occurrence of a CS-related ER visit or hospitalization, and time to mortality will be analyzed using the nonparametric Turnbull estimation method ([Turnbull, 1976](#)) for interval-censored data available in SAS PROC ICLIFETEST for each 6-month interval during Follow-up. These tables will display the number of patients still at risk at the beginning of the interval along with the number of events and censored observations within each interval. Estimates of the survival probability (the proportion of patients without the event) will be provided for the upper boundary of each interval, and these probabilities will also be displayed as figures. Estimated quartiles for event-free time (with 95% CLs) will be reported.

If death dates are available for the analysis of mortality, this analysis will be performed using the Kaplan-Meier method instead of the Turnbull method. Estimated quartiles for survival time (with 95% CLs) will be reported, and estimated survival probabilities will be displayed as Kaplan-Meier curves.

Details for all ER visits and hospitalizations, including the reason for the visit or hospitalization, will be provided in data listings.

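### One missed survey triggers automatic withdrawal, so all later survey-based outcomes are lost from patients who have not withdrawn consent

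*Protocol*

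**What the plan says.** Protocol 5.1.1 sets the schedule: "Patients will be asked to complete a survey every 6 months for up to 3 years". That gives six follow-up surveys, five of them after month 6. Protocol 6.3 adds: "One missed survey completion in the period of 1 year will automatically withdraw the patient from the study", and "unless otherwise indicated the patient will be categorized as lost-to-follow up". With two surveys due each year, a single miss is enough.

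Protocol 5.1 describes the mechanism. If the patient cannot be reached in three attempts and the window closes without a completed survey, the patient counts as lost to follow-up and "the study team will disable the patient's unique study link as appropriate". Neither document describes re-entry.

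On sources, Protocol 5.1.1 says "All assessments, except mortality, will be patient-reported". For health care use, SAP 3.2.6 says that "questionnaire items will ask patients about ER visits and hospitalizations during the prior 6-month period". Deaths follow another path (SAP 3.2.7): "Information on patient deaths during the study will be collected by the specialty pharmacy and transferred to RTI-HS for analysis". Prescription fills also come from the pharmacies, for all enrolled patients (Protocol 5.1).

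On analysis, SAP 5.1.5.1 bases each interval's incidence on patients enrolled at its start "who also provide a non-missing response to the questionnaire item for each type of event". SAP 5.2 excludes missing data everywhere except in the non-responder sensitivity analysis of the month-6 primary endpoint.

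**The concern.** A skipped survey is usually an intermittent gap. Here it becomes monotone dropout, although the patient has neither withdrawn consent nor stopped XERMELO. CS-related hospitalization and ER visits have no other routine source, and under Protocol 9.1 the same survey reports supply the study's adverse events. The exploratory objective (SAP 2.2.3) relates month-6 satisfaction to these outcomes over the study period, so it depends on the month 12 to 36 data that the rule erodes.

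At stake are the precision of the later intervals and possibly their validity. An admitted or acutely unwell patient could plausibly miss a survey and then contribute nothing further. The SAP has no sensitivity analysis for such dropout, and neither document discusses whether it is related to outcome.

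**Working it through.** **The plan's own figure.** SAP 2.4 uses an expected proportion of 50%, a half-width of 5% and 95% two-sided Wald limits: n = 1.96² × 0.5 × 0.5 / 0.05² = 384.15, rounded up to 385. With 40% dropout before month 6, 385 / 0.6 = 641.67, or 642 against the stated 643, one patient apart. This calculation stops at month 6. A missed month-6 survey is missing with or without the rule, so neither N nor the month-6 endpoints change.

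**Retention.** The documents give no non-response rate after month 6. Let m be the probability of missing any one survey, assumed independent across surveys and patients. Under the rule, a patient answers at month 36 only after answering all six surveys: (1 − m)^6. If patients may return, the share is at most 1 − m.

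| m (assumed) | With rule, (1 − m)^6 | Return allowed, 1 − m | Net loss |
|---|---|---|---|
| 5% | 74% | 95% | 21 points |
| 10% | 53% | 90% | 37 points |
| 15% | 38% | 85% | 47 points |

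**From month-6 responders.** The table applies m at month 6 too, where the SAP allows for 40% dropout. Read strictly, the analysis population (SAP 5.1.2) also needs data on at least one month-6 endpoint. Starting from the planned 385 responders with five surveys to go, month-36 respondents number 385 × (1 − m)^5 with the rule, against 385 × (1 − m) with return allowed:

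- m = 5%: 298 against 366
- m = 10%: 227 against 346
- m = 15%: 171 against 327

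**Bias.** Assume that 30% of patients are frail with a 30% event risk per interval, and the rest have 10%. True incidence is 0.3 × 0.30 + 0.7 × 0.10 = 16.0%. Others miss 10% of surveys; the frail patients' rate varies. At month 36 each group's weight is its share times (1 − m)^6 under the rule, or times (1 − m) if return is allowed.

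| Frail patients miss | Estimate with rule | Estimate, return allowed |
|---|---|---|
| 10% | 16.0% | 16.0% |
| 15% | 14.7% | 15.8% |
| 20% | 13.5% | 15.5% |
| 30% | 11.7% | 15.0% |

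Worked for 20%: the weights are 0.3 × 0.8^6 = 0.0786 and 0.7 × 0.9^6 = 0.3720, so the estimate is (0.0786 × 0.30 + 0.3720 × 0.10) / 0.4507 = 13.5%. Equal missingness gives no bias. Unequal missingness biases both designs, but the rule compounds it.

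**Recall.** SAP 5.1.5.1 plans the Turnbull estimator, which accepts intervals of unequal width. With the item limited to the preceding six months, a patient who skips month 12 and returns at month 18 reports nothing about months 6 to 12. That period is unobserved, so the item must change as well as the rule.

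**The case against.** The strongest defence is that the damage is confined and partly unavoidable. The affected outcomes are non-primary, in a study whose SAP calls all analyses descriptive. A miss requires the patient to let the window pass and not respond to up to three e-mail or telephone attempts, and someone who does so may not come back. Other exits also thin month 36. Stopping XERMELO ends participation (Protocol 5.1.1, SAP 3.2.7), and recruitment runs to 6 months before data collection ends (Protocol 6), so late enrollees have few surveys. SAP 5.1.3.1 tabulates discontinuations by time point, so attrition will be visible.

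Most of this stands. The return-allowed figures are ceilings, and the contact attempts do soften the rule. None of it supplies a reason to stop inviting a consenting patient, and a disposition table shows attrition without correcting for it.

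Four stronger readings are tempting, and the documents do not support them:

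- *All long-term outcomes are lost.* Mortality and fills come from the pharmacies. Whether deaths after survey withdrawal are counted is not stated, and the SAP 5.1.5.1 denominator leaves it unclear. That is a gap to clarify, not a documented loss.
- *Incidence is biased downward.* The documents link missed surveys to events nowhere. Independent misses cost only precision.
- *The rule removes 26%, 47% or 62% of patients.* The figure 1 − (1 − m)^6 is gross. It includes patients who would miss the month-36 survey anyway.
- *Turnbull already handles a skipped survey.* It does so only if recall spans the gap.

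Permanence is also inferred, from the disabled link and the absence of a re-entry step.

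**Conclusion.** The point holds for survey-based outcomes after month 6. As written, one skipped survey ends collection of hospitalization, ER, weight, SSA and other-therapy data from a patient who may still be consenting and on treatment. Under assumed independent misses of 5%, 10% or 15% per survey, the rule costs about 21, 37 or 47 percentage points of month-36 response. These are upper limits, because they assume full return and ignore other exits. The loss of precision follows from the rule. Downward bias in hospitalization and ER incidence is likely if sicker patients miss more surveys, but its size rests wholly on assumption. The change is worthwhile because it is cheap; the primary analysis does not depend on it.

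**What to change.** In Protocol 6.3 and 5.1, delete automatic withdrawal after one missed survey and the matching disabling of the link. Record that survey as missing. Keep inviting the patient until consent is withdrawn, the patient dies, data collection ends, or another stated exit criterion applies, including the existing one for XERMELO discontinuation.

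Reword the ER and hospitalization items to ask about events *since your last completed survey on [date]*, with the date filled in by the web survey, and align SAP 3.2.6. The Turnbull analysis in SAP 5.1.5.1 can then treat a skipped survey as a wider interval.

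The cost is a protocol amendment, continued automated invitations, a small survey change, and longer recall for patients who skipped; Protocol 5.1.1 already accepts partial dates and estimates. The gain is smaller if non-responders do not return. Since enrollment is under way, the amendment should also say how patients already withdrawn under the rule are handled.

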6.4 Criteria for Termination of the Study

If the Sponsor or regulatory officials discover conditions arising during the study that indicate that the study should be halted or that a specialty pharmacy's participation in the study should

be terminated, action may be taken at the discretion of the Sponsor. Conditions that may warrant termination of the study include, but are not limited to, the following:

- The discovery of an unexpected, serious, or unacceptable risk to the patients enrolled in the study
- A decision on the part of the Sponsor to suspend or discontinue evaluation of the product
- Failure to enroll patients into the study at an acceptable rate
- Failure to comply with pertinent Food and Drug Administration (FDA) regulations
- Submission of knowingly false information to the Sponsor, or the FDA
- Insufficient adherence to protocol requirements

Study termination and follow up would be performed in compliance with the conditions set forth in the following sections of the Code of Federal Regulations: 21 CFR 312.50 and 21 CFR 312.56.

7. Treatment

7.1 Telotristat Ethyl (XERMELO)

Treatment with XERMELO 250-mg tablets is a requirement of this study. However, XERMELO will not be supplied to participants of this study. XERMELO is available by prescription and patients are expected to take XERMELO as directed by the prescribing physician.

7.2 Prior and Concomitant Medications

7.2.1 Prior Medications

Information relating to SSA therapy, systemic tumor-directed therapy, and/or liver-directed therapy intended to treat NET, CS, individual symptoms, and/or related conditions taken by patients within 1 month of enrolling into the study will be collected.

7.2.2 Concomitant Medications

Information relating to SSA therapy, systemic tumor-directed therapy, and/or liver-directed therapy intended to treat NET, CS, individual symptoms, and/or related conditions taken by patients during the study will be collected.

7.3 Prohibited Medications or Concomitant Therapy

None

8. Study Procedures

A schedule of study assessments is provided in [Appendix A](#).

8.1 Restrictions during Study

None

8.2 Description of Study Assessments

8.2.1 Assessments

Assessments will include the following: satisfaction with CS control, CS-related diarrhea control and/or flushing control, PGIC, change in use of short-acting SSA as rescue medication, change in long-acting SSA dose or frequency, change in weight, incidence of CS-related hospitalization(s), incidence of CS-related ER visit(s), incidence of mortality, and WPAI-SHP.

All responses will be collected electronically via a web-based survey in accordance with [Appendix A](#).

A description of the study assessments is provided below.

8.2.1.1 Satisfaction with Overall Carcinoid Syndrome Control, Carcinoid Syndrome-related Diarrhea Control, Carcinoid Syndrome-related Flushing Control

Patient satisfaction with treatment prior to initiating XERMELO and satisfaction at the month 6 interval will be assessed.

8.2.1.2 Rescue Short-Acting Somatostatin Analogs (SSAs) and Long-acting SSAs

Beginning with the month 6 survey, patients will be asked to describe changes (ie, frequency, dosage) in the use of short and long-acting SSA therapy, where applicable, since initiating XERMELO.

8.2.1.3 Patient Global Impression of Change (PGIC)

At the month 6 survey, patients will be asked to describe change in overall status since the start of treatment with XERMELO.

8.2.1.4 Work Productivity and Activity Impairment – Specific Health Problem (WPAI-SHP)

At Baseline and at month 6, patients will complete the WPAI-SHP questionnaire. The WPAI-SHP has 6 items and yields 4 types of scores: (1) Absenteeism (work time missed); (2) Presenteeism (impairment at work / reduced on-the-job effectiveness); (3) Work productivity loss (overall work impairment / absenteeism plus presenteeism); and, (4) Activity impairment. WPAI-SHP outcomes are expressed as impairment percentages, with higher numbers indicating greater impairment and less productivity (ie, worse outcomes).

8.2.1.5 Change in Weight

Beginning with the month 6 survey, patients will be asked to describe perceived changes in weight, where applicable.

8.2.1.6 Incidence of CS-related Hospitalizations and Emergency Room (ER) Visit

The incidence of CS- related hospitalization and/or ER visits will be collected at Baseline and at each of the subsequent time points. Patients will be asked to provide additional information, including but not limited to the date(s), reason for each CS-related hospitalization or ER visit, action taken, outcome, dosage, and dose regimen of XERMELO.

8.2.1.7 Incidence of Mortality

The incidence of mortality will be tracked indirectly based upon information received by RTI.

8.2.2 Other Assessments

Additional information will include sociodemographic information, current medical history, height, weight, prior and concomitant medications, and prescription fill data.

8.2.2.1 Sociodemographics

Age, year of birth, sex, race, ethnicity, education, geographic region, and insurance type will be collected for all enrolled patients.

Aggregate demographic information (eg, age, sex, geographic region, insurance type) for all patients invited to participate but chose to opt-out will be provided by the specialty pharmacies in a de-identified format.

8.2.2.2 Height and Weight

Patient reported height and weight will be captured at Baseline.

8.2.2.3 Current Medical History

Patient-reported dates and diagnosis will be captured for all ongoing medical conditions related to CS, NET burden, and related conditions:

- Location of NET
- Date of diagnosis; CS and NET
- NET-related surgery (eg, tumor debulking, lysis of adhesions)

8.2.2.4 Prior and Concomitant Medications

Patients will be asked to provide information on the following taken within 1 month of study enrollment:

- Long-acting SSA therapy
- Use of rescue medication – short-acting SSA
- Systemic tumor-directed therapy
- Liver-directed therapy (eg, chemoembolization)

Patients will be asked to provide an update on therapy usage every 6 months.

8.3 Prescription Fill Data

Information regarding a patient's initial prescription fill and subsequent refill(s) will be collected.

